**A Split-Face Multi-Arm Randomized Clinical Trial
Showing the Efficacy & Safety of a Topical Mask After
Aesthetic Treatments**

[name]

A Split-Face Multi-Arm Randomized Clinical Trial Showing the Efficacy & Safety of a Topical Mask After Aesthetic Treatments.

Principal Investigator: [name]

[name]

[name]

[contact]

[contact]

Email Address: [contact]

Study Coordinator:

[name]

[name]

[name]

[contact]

[contact]

Email Addresses: [contact]

Sponsor: Velez

STATEMENT OF COMPLIANCE

The trial will be conducted in accordance with the ICH E6 and the Code of Federal Regulations on the Protection of Human Subjects (45 CFR Part 46). The Principal Investigator will assure that no deviation from, or changes to the protocol will take place without prior agreement from the sponsor and documented approval from the Institutional Review Board (IRB), except where necessary to eliminate an immediate hazard(s) to the trial participants. All personnel involved in the conduct of this study have completed Human Subjects Protection Training.

I agree to ensure that all staff members involved in the conduct of this study are informed about their obligations in meeting the above commitments.

[name]

PROTOCOL SUMMARY

Title: A Split-Face Multi-Arm Randomized Clinical Trial Showing the Efficacy & Safety of a Topical Mask After Aesthetic Treatments.

Précis: Subjects undergoing aesthetic facial treatments with either a fractionated non-ablative 1927nm Thulium laser (Sciton Moxi), ablative Erbium:Yag 2940nm (Sciton Contour), or Microneedling with Radiofrequency (Cutera Secret) will apply a face mask immediately after the procedure randomly on either their left or right side of their face with normal post-care on the other side of the face. Thirty minutes after the mask is applied to one side both regular photography and thermal photography will be done. In addition, subjects will fill out questionnaires and will be assessed by blinded evaluators for efficacy and potential side effects. Patients will wear the masks at home for at least two hours a day and return daily for photographs until deemed healed by the primary investigator (3-7 days). Patients will also fill out daily questionnaires.

Mask, Pain, Temperature, Post-Laser Care

Keywords:

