Objectives: Primary Objective: To assess the efficacy of a facial mask in decreasing facial skin temperature after three different aesthetic treatments

Important Secondary Objectives:

1. To determine the safety and incidence of adverse events when using a Velez face mask after 3 different aesthetic treatments
2. To assess the change in the level of pain when using a Velez face mask after aesthetic treatments
3. To assess patient satisfaction with use of a Velez face mask after aesthetic treatments
4. To assess erythema when using a Velez face mask after aesthetic treatments
5. To assess healing time when using a Velez face mask

Primary

Endpoints:

Primary Endpoint:

The difference between the temperature on the mid-cheek (point inferior to the lateral limbus).

Important Secondary Endpoints:

1. The difference in the number of adverse events between the two sides of the face
2. The difference in pain scores on each side of their face as rated by subjects
3. The difference in patient satisfaction scores when rating the procedure on the left and right side of their face
4. The difference in erythema on the left and right side of subject's faces as graded by blinded evaluators doing live assessments 30 minutes after the procedure
5. The difference in healing time on the left and right side of subject's faces as graded by blinded evaluators looking at daily photographs

Population: Healthy adults aged 21 and over living in Palm Beach County, Florida.

Sample Size: 15

Study Sites: [name] &
[name]

Duration: 7 days

Study Agent: Velez Intense Hydration Mask

SCHEMATIC OF STUDY DESIGN

- Total n=15
- Screen potential subjects by inclusion and exclusion criteria

Day 0 Randomization

- Obtain informed consent, randomize into one of the following two groups
- Treatment Group 1 Right Side Velez Intense Hydration Mask
- Treatment Group 2 Left Side Velez Intense Hydration Mask

Day 0 Baseline assessments/ Study Intervention

- Baseline Assessments:
 - Pre-procedure pictures taken with Canfield's imaging system (Front, Right and Left Views)
- Study Intervention:
 - 1st Arm (n=5)

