Non-ablative fractionated Thulium laser (Sciton Moxi) will be performed on level 3 and an Intense Hydration Mask will be applied to one side of the face with nothing on the other side for 30 minutes. After photos and evaluation, a hydration serum will be applied to both sides and patients will be sent home with masks to be worn at least 2 hours every day until deemed fully healed by the investigator
 - 2nd Arm (n=5)
Ablative full Erbium:Yag laser (Sciton Contour) will be performed at 200 microns and an Intense Hydration Mask will be applied to one side of the face with nothing on the other side for 30 minutes. After photos and evaluation, Vaseline will be applied on both sides of the face and the patient will be sent home with masks to be worn at least 2 hours every day until deemed fully healed by the investigator
 - 3rd Arm (n=5)
Microneedling with RF (Cutera Secret) will be done with a non-insulated needle at a depth of 200 and an Intense Hydration Mask will be applied to one side of the face with nothing on the other side for 30 minutes. After photos and evaluation, a hydrating serum will be applied on both sides of the face and the patient will be sent home with masks to be worn at least 2 hours every day until deemed fully healed by the investigator

All Arms

- Post-procedure pictures and questionnaires to be completed by subjects 30 minutes after the procedure
- Safety analysis and erythema scale to be performed by blind evaluators and a compliance analysis performed by study coordinator

Day 1-7 Follow-up assessments

- Daily in office follow-up assessments of study endpoints and safety until primary investigator deems patients healed from the procedure

1st Arm (n=5) Non-ablative fractionated Thulium laser (Sciton Moxi)

Post-procedure pictures and questionnaires to be completed by subjects for 3-7 days as determined daily by the primary investigator

2nd Arm (n=5) Ablative full Erbium:Yag laser (Sciton Contour)

Post-procedure pictures and questionnaires to be completed by subjects daily for 3-7 days as determined daily by the primary investigator

3rd Arm (n=5) Microneedling with RF (Cutera Secret)

Post-procedure pictures and questionnaires to be completed by subjects daily for 3-7 days as determined daily by the primary investigator

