3 STUDY DESIGN, OBJECTIVES, AND ENDPOINTS

3.1 DESCRIPTION OF THE STUDY DESIGN

- A Prospective, Multi-Arm, Split-Face, Randomized Clinical Trial
- 2 Study Centers
- Study agent: Velez Intense Hydration Mask
- Study Intervention on Day 0
- Live evaluations by Blinded Evaluators on Day 0
- Daily photographic evaluations by Blinded Evaluators

This will be a prospective, multi-arm, evaluator blind, split-face, clinical trial in which subjects will be randomized to 2 groups in 3 separate arms.

1st Arm (n=5) Non-ablative fractionated Thulium laser (Sciton Moxi)

2nd Arm (n=5) Ablative full Erbium:Yag laser (Sciton Contour)

3rd Arm (n=5) Microneedling with RF (Cutera Secret)

In each arm, there will be two groups

1st group: Velez Intense Hydration Facemask on the left side of their face and nothing on the right

2nd group: Velez Intense Hydration Facemask on the right side of their face and nothing on the left side

Both groups will be utilizing the same safety and comfort protocols established by the practice which include the use of topical numbing cream (B.L.T.) before the laser procedure and cleansing with a makeup wipe and alcohol.

After the procedure a blind evaluator will be grading the subjects' erythema, edema, and any side effects. A compliance analysis performed by study coordinator will be done each visit.

Thirty minutes after the laser procedure, digital photography using Canfield's imaging system, and a thermal camera will be done. In addition, a subject questionnaire on satisfaction, erythema, edema and pain levels after the procedure will be completed. Patients will then have the typical post-care treatment on both sides of their face such as Vaseline for laser resurfacing and a hydrating serum for the Moxi and Microneedling. They will apply the mask at home for at least two hours each day and then return to the office daily for questionnaires and photographs until deemed fully healed by the primary investigator.

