3.2.2 SECONDARY ENDPOINTS

- The difference in the number of adverse events between the two sides of the face
- The difference in pain scores on each side of their face as rated by subjects
- The difference in patient satisfaction scores when rating the procedure on the left and right side of their face
- The difference in erythema on the left and right side of subject's faces as graded by blinded evaluators doing live assessments 30 minutes after the procedure
- The difference in healing time in daily photographs as rated by blinded evaluators

These endpoints will show if the Velez Intense Hydration face mask decreases skin temperature after a cosmetic procedure, if subjects are happy with the use of the mask, and if they provide significant reduction in pain, erythema, and healing time.

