6.3.3 FOLLOW -UP

Follow Up Visits (Visit 2-8, Day 1-7)

- Record adverse events as reported by participant on side assigned the mask
- Photograph with both thermal camera and Canfield standardized photography
- Primary investigator to advise each day if they need to return the next day or are done with the study and completely healed

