6.3.7 SCHEDULE OF EVENTS TABLE

Procedures	Screening	Enrollment/Baseline Visit 1, Day 0	Day 1	, Day 2-	, Day 3-	, Day 4-	, Day 5-	, Day 6-	, Day 7-
Informed consent & Randomization		X							
Demographics & Medical History		X							
Aesthetic Treatment		X							
Subject Questionnaire	X	X	X	X	X	+/-X	+/-X	+/-X	+/-X
Exam for Adverse Effects		X	x	x	x	+/- x	+/- x	+/- x	+/- x
Exam by blinded Evaluator		X							
Intervention with Face Mask		X	x	x	x	+/- x	+/- x	+/- x	+/- x
Photos		X	x	x	x	+/-x	+/-x	+/-x	+/-x

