8.2 STATISTICAL HYPOTHESES

Primary Endpoint

- The alternative hypothesis is the difference in the mean temperatures on each side of the face is greater than zero
- The null hypothesis is the difference in the mean temperatures on both sides of the face is zero.

Secondary Endpoints

1.

- The alternative hypothesis is the difference in the mean pain, erythema, and comfort scores from one side to the other side is greater than zero
- The null hypothesis is the difference in the mean pain, erythema, and comfort scores from one side to the other side is zero.

All other secondary effectiveness analyses will be done descriptively as appropriate.

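### Does healing time per side need a written definition, a rule for a side never graded healed, and a test?

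*Combined protocol and SAP*

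**What the plan says.** The protocol summary lists the left-right difference in healing time as the fifth secondary endpoint, "as graded by blinded evaluators looking at daily photographs". Section 3.1 lists "Daily photographic evaluations by Blinded Evaluators" among the design features, and section 3.2.2 repeats the endpoint. In the schedule of events (6.3.7) the row "Exam by blinded Evaluator" is marked on Day 0 only, so later side-specific healing data come from the photographs.

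The photographs end on the judgement of someone else. In section 6.3.3 it is for the "Primary investigator to advise each day if they need to return the next day or are done with the study and completely healed". The schematic likewise has masks worn "until deemed fully healed by the investigator". The decision is made once per patient, and the schedule ends at Day 7.

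On inference, section 3.2.2 says the endpoints will show, for the masks, "if they provide significant reduction in pain, erythema, and healing time". Section 8.2 states secondary hypotheses for pain, erythema and comfort only, and then adds: "All other secondary effectiveness analyses will be done descriptively as appropriate". Section 8.6 repeats that sentence, after applying a paired t-test to two secondary endpoints that it does not name. Section 8.4 provides only for counting and reporting missing values.

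**The concern.** Three things look unfinished.

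- No section tells the evaluators what they must see in a photograph to call a side healed.
- The evaluators grade each side, but the investigator ends the series for the whole patient, and Day 7 ends it in any case. A side they have not graded healed at its last photograph has no observed healing day. The analyst could count the last photograph as the healing day, assign a later day, or drop the pair.
- Section 3.2.2 uses the language of significance for an endpoint that has no hypothesis in section 8.2.

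If the mask works, the unobserved day falls mostly on the slower, unmasked side. Counting the last photograph as healed, or dropping the pair, would then tend to shrink the side difference. With 15 subjects, one or two pairs could matter to a test. In an exact two-sided sign test, 10 of 12 untied pairs gives p = 0.039 and 9 of 12 gives p = 0.146.

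**Working it through.** **What the plan gives.** There is no effect size, SD, power or sample size for healing time, so there is no figure to reproduce. The 4.343 in section 8.6 (21.021/4.84) concerns cheek temperature. The only healing input is the range of 3-7 days in the summary.

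**Status of the endpoint.** Section 8.2 names three scores and makes every other secondary effectiveness analysis descriptive. Healing time is not among the three, so it is descriptive. The sentence in 3.2.2 is a statement of purpose and specifies no test. The unnamed two endpoints in 8.6 are a separate looseness, and 8.6 itself repeats the descriptive default.

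**Size of the Day 7 effect (illustration).** The assumptions are:

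- healing times are bivariate normal and recorded on the next whole day;
- SD is 1.2 days on each side;
- the masked side heals 1.0 day earlier;
- the between-side correlation runs from 0 to 0.9;
- photographs continue until the slower side is graded healed, but not beyond Day 7.

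A side is ungraded if its time exceeds 7.

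*Unmasked recorded mean 5.0, the midpoint of 3-7 (4.5 before rounding up):*
- Unmasked side: 1 − Φ((7 − 4.5)/1.2) = 1 − Φ(2.083) = 0.0186.
- Masked side: 1 − Φ((7 − 3.5)/1.2) = 1 − Φ(2.917) = 0.0018.
- At least one side, correlation 0: 0.0186 + 0.0018 − 0.0186 × 0.0018 = 0.0203. At high correlation it falls to about 0.0186.
- Expected number among 15: 15 × 0.0186 = 0.28 to 15 × 0.0203 = 0.30.
- Chance of any among 15: 1 − (1 − 0.0186)^15 = 25% to 1 − (1 − 0.0203)^15 = 27%.

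*Unmasked recorded mean 6.0 (5.5 before rounding up):*
- Unmasked side: 1 − Φ(1.25) = 0.1056. Masked side: 1 − Φ(2.083) = 0.0186.
- At least one side: 0.106 to 0.122, or 1.6 to 1.8 of 15 subjects.

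Simulation of 1,000,000 subjects per setting gives the reading of a true 1.0-day difference:

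| Recorded mean, unmasked | Subjects with an ungraded side | Last photograph counted as healed | Pair dropped |
|---|---|---|---|
| 5.0 | about 2% | 0.98 | 0.95-0.99 |
| 6.0 | 11-12% | about 0.90 | 0.80-0.96 |

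**Would a ranking rule and a new test help?** One could rank an ungraded side later than its last photograph and add an exact two-sided sign test with ties dropped. Two-sided 5% power with 15 subjects in the same simulation:

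| Correlation | Sign test, ranked | Sign test, last photograph as healed (mean 6.0) | Paired t-test, last photograph as healed (mean 6.0 / 5.0) |
|---|---|---|---|
| 0 | 34% | 34% | 53% / 54% |
| 0.5 | 63% | 61% | 78% / 81% |
| 0.8 | 95% | 93% | 98% / 99% |
| 0.9 | over 99% | 99% | over 99% / over 99% |

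Ranking gains at most about 2 points over the simplest handling. The sign test gives up about 15-20 points against the paired t-test at correlations 0 to 0.5. Within one arm of 5 the sign test cannot reach 0.05 at all, since its smallest two-sided p is 2 × 0.5^5 = 0.0625.

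**The case for a change.** The strongest reply is that the illustration covers only the Day 7 limit. It lets photographs run until the slower side is graded healed, so it sets disagreement between the investigator and the evaluators to zero, and that disagreement is the weak point of the 6.3.3 arrangement. Any earlier stop would add ungraded sides. This stands as a limit on the figures. The documents give nothing from which to estimate how often it would happen. Reading completely healed as both sides healed narrows the room for it without closing it.

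A second reply is that the choice of handling can move the answer. Take five invented subjects with masked-side days 4, 5, 5, 6, 6 and unmasked-side days 5, 6, 7, plus two unmasked sides still ungraded on Day 7. The mean difference is 1.2 days (p = 0.004) with the last photograph counted as healed, 1.6 (p = 0.003) with one day added, 2.4 (p = 0.024) with Day 10 assigned, and 1.33 (p = 0.057) with the two pairs dropped. The arithmetic is right, but two of five is 40% ungraded, far above the 2-12% in the illustration. The p-values would also bear on a conclusion only if healing time were tested.

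A third reply is that wording costs nothing. That is true, and a written criterion for a healed side would be tidier. It still would not correct any result that the plan produces as it stands.

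**Conclusion.** No change follows. The healed criterion and the record for an ungraded side are conventions left unwritten for one descriptive secondary endpoint, and no rule that is written gives a wrong answer. Analysts can fill the gap sensibly by listing the healing day by side, marking a side not graded healed at its last photograph as such, and giving the number, in keeping with the count of missing values in section 8.4. The significance wording in 3.2.2 is loose drafting. Section 8.2 governs, and removing the word would alter no analysis. A sign test would be a debatable addition with less power than the paired t-test already named in 8.6.

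The size rests on assumed values: SD 1.2 days, a 1.0-day benefit, whole-day grading, and one healing distribution for all three procedures. On those, about 0.3 of 15 subjects are affected if healing centres on Day 5, and 1.6-1.8 if it centres on Day 6, which nothing in the documents supports over Day 5. Disagreement between investigator and evaluators before Day 7 is not quantified. The primary temperature endpoint is untouched.

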6.2.2 ENROLLMENT/BASELINE

Enrollment/Baseline Visit (Visit 1, Day 0)

- Review in depth the study design with subjects and obtain informed consent of potential participants verified by signature
- Perform examination and verbally review subject's medications and medical history to determine eligibility based on inclusion/exclusion criteria.
- Verify all inclusion/exclusion criteria.
- Obtain demographic information
- Randomization
- Perform either a Sciton Moxi, Sciton Erbium, or Secret RF treatments to subject's face, and then apply a half mask on one side of the face according to randomized groups.
- Record adverse events as reported by participant or observed by investigator or blind evaluator.
- Perform protocol adherence check by study coordinator
- Collect post-procedure subject questionnaires
- Take post-procedure photos

- After photographs and blind evaluation both side of the face will be treated with the normal post-procedure care such as Vaseline for laser resurfacing and a Hydrating serum for Moxi and Microneedling. Additional masks will be given to patients to wear for 2 hours at home each day until deemed healed by the primary investigator.

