8.7 MEASURES TO MINIMIZE BIAS

8.7.1 ENROLLMENT/ RANDOMIZATION/ MASKING PROCEDURES

To avoid bias, the subjects will be randomized to receive the treatment on one side. All evaluators will be blinded as to which side received the active intervention. The blinded evaluators will observe the subjects, but both the evaluator and subjects will be told that no discussions are to take place between the two and that the subjects are to remain silent during the evaluator examination.

To ensure only the clinical investigator performing the procedures and the study coordinator know the assignment, each subject will have an envelope assigned to them to be held by the study coordinator with the subject's name on the outside and the assignment on the inside. Only after the laser treatment does the study coordinator allow the clinical investigator to see the inside of the envelope with the randomized group assignment.

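### Healing time is graded blind for each side of the face, but the photographs it rests on stop at one whole-subject call by the primary investigator

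*Combined protocol and SAP*

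**What the plan says.** The Protocol Summary defines the fifth secondary endpoint as "The difference in healing time on the left and right side of subject's faces as graded by blinded evaluators looking at daily photographs". Section 3.2.2 repeats it as "The difference in healing time in daily photographs as rated by blinded evaluators". In the schedule of events (6.3.7) the row "Exam by blinded Evaluator" is marked on Day 0 only, so blinded grading after Day 0 depends on the photographs.

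The length of the photograph series is set elsewhere. The study schematic provides for "Daily in office follow-up assessments of study endpoints and safety until primary investigator deems patients healed from the procedure". The précis gives the same stopping rule for the photographs and a range of 3 to 7 days. Section 6.3.3 assigns the decision: "Primary investigator to advise each day if they need to return the next day or are done with the study and completely healed".

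On masking, section 8.7.1 blinds all evaluators and aims to ensure that "only the clinical investigator performing the procedures and the study coordinator know the assignment". It does not mention the primary investigator by that title. On missing data, section 8.4 says only that missing values will be counted and reported.

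**The concern.** The outcome is recorded per side, by blinded readers. Its observation window is set per subject, by a person outside that reading process. No section requires the blinded evaluators to have graded both sides healed before photography ends, so they can never record a healing day later than the day of the investigator's call. If the slower side is still unhealed in their view on that day, its healing time is not observed.

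Sections 2.2 and 3.2.2 say the trial will show whether the mask shortens healing. With five subjects per arm, one or two cut-off series can visibly change an arm's mean difference, even if that mean is only described. Photographs that were never taken cannot be recovered at analysis.

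**Working it through.** The plan states no figure for healing time, so there is nothing to reproduce. The check is a comparison of the texts, then a short derivation, then an illustration under assumed inputs.

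**1. Texts side by side**
- Unit of the endpoint: each side of the face (Protocol Summary). Unit of the stopping call: the subject (schematic, 6.3.3).
- Who grades: blinded evaluators, from photographs (Protocol Summary, 3.2.2). Who stops: the primary investigator (précis, schematic, 6.3.3).
- Link between the two: none stated.
- Rule for a side not graded healed at the last photograph: none (8.4).

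**2. Direction of the effect**

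Let T be the day on which the blinded evaluators would grade a side healed, and C the day of the call. If the last photograph is taken as healed, the recorded day is min(T, C). C is the same for both sides, so

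|min(T₁, C) − min(T₂, C)| ≤ |T₁ − T₂|,

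and the sign cannot reverse. The difference can shrink, possibly to zero, but cannot grow. The largest recordable difference is C − 1: 2 days for a call on Day 3, and 6 days for a call on Day 7.

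Example with assumed healing days of 4 and 6 (true difference 2):
- call on Day 4: min(6, 4) − min(4, 4) = 0
- call on Day 5: 5 − 4 = 1
- call on Day 6: 6 − 4 = 2

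**3. Possible size**

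The documents give no mean, spread, mask effect or reader disagreement for healing time. All inputs here are assumptions: mean healing day 4, SD 1 day between subjects and 0.5 day per side, a mask effect of 1 day, and a call between Day 3 and Day 7, made when both sides look healed to the investigator. The investigator's judgement differs from the graders' with a given SD, independently for each side. Healing day is rounded up to the next visit. With 200,000 simulated subjects per scenario and a true difference of about 0.99 to 1.00 day:

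| Disagreement SD (days) | Difference seen (days) | Subjects with a side cut off |
|---|---|---|
| 0 | 0.98 to 0.99 | about 1% or fewer |
| 0.25 | 0.91 to 0.92 | not quoted |
| 0.5 to 1 | 0.80 to 0.86 | roughly 15% to 22% |

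The ranges cover repeat runs with small differences in set-up. If the same error applies to both sides of a subject, the last row becomes about 0.75 to 0.84 day, with 19% to 30% cut off. The loss therefore comes almost wholly from assumed disagreement between the investigator and the graders.

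**The case against.** The best defence is the wording of 6.3.3, which requires the subject to be completely healed. The natural meaning is both sides. An investigator who applies that and agrees with the graders loses almost nothing, as the zero-disagreement row shows. This stands, and it limits the size of the point. It does not remove it, because nothing requires the two judgements to agree and nothing says what to do when they do not.

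The consequence is also limited. Healing time is the last of five secondary endpoints. Section 8.2 states hypotheses for pain, erythema and comfort and leaves the other secondary effectiveness analyses descriptive. No stated test or sample size depends on it.

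A reader might infer several stronger things that the documents do not support:
- **That the blinding of the endpoint is undone.** Nothing in the follow-up rule shows the graders which side had the mask. This is censoring, not unblinding, and cutting both sides at the same day cannot create a false mask benefit.
- **That the primary investigator knows the side.** Section 8.7.1 limits the assignment to the operator and the coordinator. The documents do not say whether the primary investigator is the operator. The Day 0 line in 6.2.2, "Record adverse events as reported by participant or observed by investigator or blind evaluator", concerns adverse-event recording and does not settle it. Knowledge of the side is possible, since 6.3.3 records adverse events on the mask side and 7.5 has the principal investigator record events with affected area and relation to product. It is not established.
- **That most of the effect is lost.** Under the same assumptions the difference seen falls to 0.52 to 0.53 day if the call follows the overall look of the face, and to 0.21 to 0.31 day if it follows the masked side. Both have the investigator releasing subjects with an unhealed side, against the wording of 6.3.3.
- **That subjects may be released from Day 1.** Read alone, 6.3.3 allows this. The 3 to 7 days in the précis and schematic, with the fixed Day 1 to 3 visits in 6.3.7, largely answer it.

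**Conclusion.** The point holds as a censoring problem. A blinded, per-side outcome is cut off at a single whole-subject judgement that is not tied to the blinded grades, made by a person whom no section states to be blinded. If the last photograph is taken as healed, the bias is toward no difference. Its size cannot be derived from the documents. With the assumed inputs and the both-sides reading, 0.99 day is seen as about 0.80 to 0.86 day, and nearly the full difference is kept if investigator and graders agree. The endpoint is secondary and appears to be descriptive, and the 30-minute temperature comparison is untouched. Severity is low to moderate. The change is a cheap improvement that has to be settled before enrolment.

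**What to change.** In 6.3.3 and the précis, continue each subject's photographs until the blinded evaluators have graded both sides healed or until Day 7, whichever comes first. The simpler alternative is to photograph every subject through Day 7. Keep the primary investigator's call for clinical care only. The home mask instruction is tied to the same call, and this change does not touch it. In section 8.4, state that a side not graded healed at the last photograph is reported as censored at that day, not as healed, and give the number of such sides by arm and by masked or unmasked side.

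Cost: under the first option, the existing evaluators grade on a rolling basis, in time for each next-day visit decision at two centres, instead of in one batch. Under the second, up to four extra visits per subject (Days 4 to 7), so at most 4 × 15 = 60 in total, all within the existing Day 7 window. Neither needs more subjects or readers.
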